		10.1 Study Database
		Introduction of Microsoft OneDrive as a central data repository
		12.1 Objective measures of disease Introduction of blinded central reader to determine mLK scores
		13.1 Missing data handling
		Introduction of multiple imputation approach
		13.6 Primary Analysis
		Strategy for handling of intercurrent events is further described
		13.7 Secondary and Exploratory Analysis
		Revision surgery during follow-up will be considered a treatment
		failure
		14.3 Recording and Reporting Adverse Events
		Reporting expectations are clarified, to include 24-hour notification
2.3	02 Mar 2021	6.1 Overall Design
	021/1012021	Background medication changed from Budesonide irrigations to
		standard of care intranasal corticosteroid sprays (INCS), as chosen
		by the treating physician
		8.1.2 Non-Investigational Products
		Background medication changed from Budesonide irrigations to
		standard of care intranasal corticosteroid sprays (INCS), as chosen
		by the treating physician
		8.3.5 Rescue Therapy
		Topical corticosteroid irrigations allowed as rescue per treating
		physician
2.4	12 Nov 2021	Table 1: Schedule of Activities
		Defined frequency of pregnancy testing and assessment of subject
		compliance
		4.6.3 Accountability
		Westat included as external study monitor with defined monitoring
		plan

		4.8 Pharmacy
		Belmar Pharma Solutions included as dispensing pharmacy
		8. Study Timelines
		Updated timeline for study milestones
		16.2 Database Set-up and Management
		Inclusion of FDA Part 11 compliance
		17.1 Obligations of Sponsor-Investigator
		Inclusion of 21 CFR 312
		17.4.3 Evaluation of Causality
		Defined IND Safety Reporting
3.0	28 Dec 2021	Protocol Formatting
		Clarification provided to define protocol mandated study activities
		versus those completed per standard of care (sinus surgery, nasal
		saline irrigations, topical corticosteroid sprays)
		1.0 Study Summary
		Addition of reminder text messages the day of scheduled IMP
		injections.
		Table 4: Investigational study treatments
		Clarification of Placebo
		4.6 Preparation/handling/administration/accountability
		Description of central pharmacy and delivery of study drug, as well
		as internal monitoring for drug receipt and subsequent use / disposal
		Appendix C: Data and Safety Monitoring Board Charter
		DSMB Charter included
		Appendix E: List of Study Vendors
		Reference list of study vendors included
3.1	31 Jan 2022	15.4.1 Evaluation of Severity
3.1	31 Jan 2022	Addition of Common Terminology Criteria for Adverse Events
3.2	17 Feb 2022	(CTCAE) to evaluate AE event severity Title:
3.2	17 Feb 2022	
		Added S-I
		1. Study Summary
		Addition of SNOT-22 and ACT in the table
		6. Data Specimen Banking
		Changed "mandatory" to "optional"
		7.1 Inclusion Criteria
		Added the language that non-English speakers will be included
		7.1.5 Reproduction
		Added men criteria

3.3	31 May 2022 28 Jun 2022	3. Study Objectives and Endpoints Addition of co-primary endpoint 15.3 Recording and Reporting Adverse Events Added details for clarification Copied a section about FDA reporting (that was initially under 15.4 Evaluation of Severity and Causality) 14.6 Primary Analysis Added specific details about the statistical model analysis for subject with unilateral disease plan for Type I error control
3.4	14 Jul 2022	14.11 Safety evaluation plan Added 1. Study Summary Removed Randomization from visit 3 and added it to surgery period. Clarified Surgery period length: 7 days ± 4 weeks Study design is summarized in Figure 1 Updated the Figure with correct running timeframe 4.1 Overall Design Clarified that randomization is before visit 3 (week0) 15.7 Monitoring Table 2 Added to this version
3.5	9 Aug 2022	2. Background Added more details on dupilumab mechanism of action and rationale. 4.6.2 Administration Clarified that participants who prefer to get injection at the clinic can do so. 13. Compensation Clarified how compensation will be done at study visit
3.6	7 Mar 2023	Appendix D: List of Study Personnel Addition of Removal of 5.2.1 Objective measures of disease Incentive Spirometry: Removed "Incentive" to reflect the correct procedure 6. Data Specimen Banking Renamed this section "Data Specimen collection and Banking" to clarify that the specimen is not only for banking. Rearranged the section to explain the required collection first and then the optional. Appendix E: List of Study Vendors Changed Westat contact person to [name]
3.7	21 Mar 2023	Investigators Added as PI of Emory site.

		Changed (S-I) address to the NIH site
		Across the protocol
		Added the fourth site: NIH and changed the number of sites from
		three to four, and the number of participants per site from 44 to 33.
		Removed RSDI to be consistent with the SoA
3.7.1	1 Sep 2023	Across the protocol
		Removed Vanderbilt as a site and changed the number of sites from
		four to three, and the number of participants from 33 to 44.
		Clarified that study visits and dosing of IMP can be within 7 days
		of planned date in line with prescribing package information for
		dupilumab for CRSwNP.
		1
		Formatting adjustments. Subjects updated to participants
		Standardized treatment for nasal polyps to daily include saline
		irrigations and INCS spray.
		Standardized that pregnancy test will be done until visit 8
		Table 1.
		Clarified that CT scan is per SoC and can be up to 6 months before
		surgery.
		Clarified that randomization occurs post-operatively
		4.5.3 Postoperative care / 7.1.4 Sinus Surgery
		Post operative pain regimen at discretion of treating physician.
		Oral steroid regimen specified to be prednisone.
		Removed from section 7.1.4 (duplicated information)
		4.7 Randomization and blinding
		Randomization, blinding, and emergency unblinding provided by
		study data team
		6. Data Specimen Collection and Banking
		Clarified that routine laboratory monitoring is not planned but can
		be obtained for SoC if needed
		7.2.1. Exclusion Criteria
		Removed mucocele as exclusion criteria as this frequently seen in
		AFRS.
3.7.2	9 Oct 2023	Schema
3.7.2	7 001 2023	Updated the schema to reflect the changes made to the protocol
272	2 App 2024	
3.7.3	2 Apr 2024	Across the protocol
		Asthma Control Test (ACT) was replaced by Asthma Control Questionnaire (ACQ) throughout the protocol.
		4.1 Overall Design Protocol election to allow appellment of participants within 2
		Protocol clarified to allow enrollment of participants within 2
		weeks of surgery if they have been on background therapy for a
		minimum of 2 weeks and meet all other eligibility criteria.

Protocol Title: S-I: Add-on Dupilumab for AFRS as Postoperative Therapy (ADAPT)

Table of Contents

1.	Study Summary	8
2.	Background	
3.	Study Objectives and Endpoints	
4.	Study Intervention/Investigational Agent	
5.	Procedures Involved	22
6.	Data Specimen Banking	24
7.	Inclusion and Exclusion Criteria	24
8.	Local Number of Participants	27
9.	Recruitment Methods	28
10.	Withdrawal of Participants	28
	Risk to Participants	
12.	Potential Benefits to Participants	28
13.	Compensation to Participants	29
	Data Management and Confidentiality	
15.	Provisions to Monitor the Data to Ensure the Safety of Participants	33
	Provisions to Protect the Privacy Interest of Participants	
17.	Informed Consent	40
18.	Setting	40
19.	Appendix	41
20.	Resources Available	58
21.	Multi-Site Research monitoring	58
22	References	50

1. Study Summary

Table 1: Schedule of Activities

	Run-	Surgery Randomized Treatment period						EOT	EOS			
	in											
Visita	1	2	3		4		5		6		7	8
Week	W-6	W-1	W0	2,4,6,8,10 ^b	12	14,16,18,20,22 ^b	24	26,28,30,32, 34 ^b	36	38,40,42,44,46,48, 50 ^b	52	64
Day ± 7	D-42	D-7g	D0		D84		D168		D252	_	D364	D448
Informed consent	X											
Inclusion and exclusion criteria	X		X									
Patient Demography	X											
Medical / surgery history	X											
Physical exam	X		X		X		X		X		X	X
Urine Pregnancy Test ^c	X		X		X		X		X		X	X
Transfer diagnostic nasal endoscopy to online repository	X		X		X		X		X		X	X

D	37		37		37		37		37		37	37
Determination of			X		X		X		X		X	X
mLK endoscopic												
score ^d												
Spirometry ^e	X		X		X		X		X		X	X
SNOT-22	X		X		X		X		X		X	X
ACQ	X		X		X		X		X		X	X
CT sinus scan	X^{i}										X	
Randomization		X										
Collect	X		X		X		X				X	X
peripheral												
bloodh												
Sinus mucus	X		X		X		X				X	X
sampleh	1											
Ethmoid sinus		X										
tissue												
Treatment:										. 		
IMP:			X	X	X	X	X	X	X	X		
Dupilumab/												
placebo												
injection ^b												
Record	X	X	X		X		X		X		X	X
concomitant												
medications												
Text reminder				X, X, X, X,		X, X, X, X, X		X, X, X, X,		X, X, X, X, X, X,		
for IMP self-				X		11, 11, 11, 11, 11		X		X		
administration ^b				11						11		
Assessment				X, X		X, X		X, X		X, X, X		
of IMP				21, 21		71, 71		71, 71		71, 71, 71		
compliance												
(phone												
call) ^b												
Caii)												

Assessment of IMP			X	X	X	X	
compliance							
(device							
collection)b							
Record planned							
surgery for NP,							
OCS use and		 	 	 X	 	 	
other rescue							
medications							

^a Patients who discontinue treatment early will be assessed as soon as possible using the procedures normally planned for the EOT Visit.

ACQ: Asthma Control Questionnaire, AE: Adverse Event, CT: Computed Tomography, IMP: Investigational Medical Product, mLK: Modified Lund Kennedy Endoscopic Score, NP: Nasal Polyp, OCS: Oral Corticosteroid, SAE: Serious Adverse Event, SNOT-22: 22-item SinoNasal Outcomes Test, WOCBP: women of childbearing potential

^b Patients will self-administer investigational drugs between study visits (v3-8). Compliance will be ensured by reminder text messages the day of each home injection, monthly phone calls and collection of injection materials at following study visits.

^c Urine pregnancy test completed by all WOCBP, (i.e., post-pubescent, premenopausal females).

^d Determination of mLK endoscopic scores will be completed by a blinded, central reader for all study sites.

^e Lower airway assessments completed for participants with medical history of comorbid asthma (~25% of study cohort).

^f Patients will be randomized once pathology report is available post-operatively to confirm presence of fungus.

^g Surgery period can be extended to 4 weeks to accommodate operating room availability, unforeseen personal events, or other occurrences that delay randomization.

^h Optional, only in participants that consent to collection and banking of these materials.

ⁱ If not previously obtained within prior 6 months.

Project Title	S-I A randomized, 52-week treatment double-blind, placebo-controlled efficacy and safety study of dupilumab 300 mg every other week after endoscopic sinus surgery in participants with allergic fungal rhinosinusitis (AFRS) on a background therapy with intranasal corticosteroid spray Short: Add-on Dupilumab for AFRS as Postoperative Therapy (ADAPT)				
Project Design	Multicenter, randomized, double-blind, placebo-controlled study comparing the efficacy of dupilumab to placebo in allergic fungal rhinosinusitis (AFRS) participants after sinus surgery on a background treatment with intranasal corticosteroid spray				
	Study periods: The clinical trial consists of 4 periods: 1. Run-in period (2 weeks + 4 weeks): All participants will enter a run-in period of 2-6 weeks receiving saline irrigations and INCS spray daily. All oral steroids and antibiotics as well as corticosteroid rinses will be stopped. 2. Surgery period (7 days + 4 weeks): Patients will undergo surgery as scheduled. Sinonasal mucus, peripheral blood and ethmoid tissue will be collected from all participants at the time of surgery. 3. Randomized treatment (52 weeks ± 7 days): Patients will be randomized to one of the following treatments: • Arm A: dupilumab 300 mg subcutaneous (SC) q2w until Week 52 • Arm B: placebo given SC q2w until Week 52 4. Posttreatment period (12 weeks ± 3 days): After completing 52 weeks of treatment with IMP (or following early discontinuation of IMP or discontinuation from the study), participants will be instructed to • Return to the study site for the last scheduled visits for physical examination, nasal endoscopy, NPS, PROs (SNOT-22 and ACQ), FEV1 measurement in those with asthma and safety. • Continue on stable dose of INCS spray during the posttreatment period.				
	Report any adverse event (AE).				
Co-Primary Objectives	 a) Determine the efficacy of dupilumab in controlling sinonasal inflammation and preventing nasal polyp recurrence after complete sinus surgery for AFRS, as measured by change in the mLK score b) Evaluate the effect of dupilumab on oral corticosteroid utilization following complete sinus surgery for AFRS 				
Secondary	To evaluate the effect of dupilumab on:				
Objectives	Prevention of revision surgery for AFRS				
Objectives	 				
	 Secondary objective measures of sinonasal inflammation following sinus surgery using the NPS and LMS 				
	 Lower airway dysfunction following sinus surgery in the subgroup of 				
	participants with asthma (~25%)				
	Upper and lower airway, disease-specific, health-related quality of life, as				
	measured by ACQ and SNOT-22				
	Reducing utilization of rescue medications for acute exacerbations of CRS following sinus surgery				

Research Interventions / Interactions	Matching placebo w receive a total of 26 pharmacy, with com scheduled home adn collection at recurrin IMP will be complet 10, 14, 16, 18, 20, 22 in WOCBP will be of All participants will corticosteroid sprays throughout the entire up to 40-50%, which	doses of IMP. Patients will apliance assessments via reministration, as well as monting 3-month study visits (Woted at home to maintain a 2-2, 26, 28, 30, 32, 34, 38, 40, completed during each study undergo standardized backges (INCS) per standard of care study. The systemic bioavant is why we will standardized	ery 2 weeks with an EOT at we same time points. Patients wereceive IMP directly from the ninder text messages the day hly phone calls and injection 1, 12, 24, 36). Self-administrative week treatment schedule (W. 42, 44, 46, 48, 50). Pregnant wisit (W0, 12, 24, 36, 52, 64 ground therapy with intranastive (SoC). This will be continually allability of INCS varies from the dose of INCS. Participates one furoate at the following	will the central of each a device ation of 2, 4, 6, 8, cy testing 4). al ued m <1% to nts will	
	INCS	Frequency	Total Daily Dosage		
	Fluticasone propionate	2 sprays (50mcg) in each nostril once daily	200mcg		
	Mometasone 2 sprays (50mcg) in furoate each nostril twice daily				
Study Population Sample Size	Allergic Fungal Rhi		an sites. A total of 132 partic	cinants will	
	be randomized.		an sites. It total of 132 partie	Tpunts will	
Study Duration for individual participants	The total duration of the study (per subject) is expected to be approximately 71 weeks: • Run-in period (2-6 weeks*) • Surgery period (7 days + 4 weeks) • Randomized treatment period (52 weeks ± 7 days) • Posttreatment period (12 weeks ± 3 days) *Participants may be consented & enrolled at any time during run-in or presurgical period, provided the failure of appropriate medical therapy has been documented as outlined in the inclusion criteria				
Study Specific Abbreviations	Abbreviation or Term	Definition			
/ Definitions	ACQ AE AERD	Asthma Control Questionna Adverse event Aspirin exacerbated respira Morning			
1	AFDC	A11 ' E 1 D1' '	•,•		

[figure not shown]
Allergic Fungal Rhinosinusitis

Version: 3.7.3 2Apr2024

AFRS

	1	
	BID	Twice a day
	CFR	Code of Federal Regulations
	CRSwNP	Chronic Rhinosinusitis with nasal polyps
	CT	Computed tomography
	EDC	Electronic Data Capture
	FU	Follow-up
	GCP	Good clinical practice
	ICF	Informed consent form
	IMP	Investigational medicinal product
	INCS	Intranasal corticosteroids
	IP	Investigational product
	IPD	IP discontinuation
	IRB	Institutional Review Board
	LMS	Lund-Mackay score
	mLK	Modified Lund Kennedy Endoscopic Score
	SNOT-22	SinoNasal Outcome Test, 22 item
	SoC	Standard of Care
	WOCBP	Women of childbearing potential
Funding	Sanofi	
Source		

Schema

2. Background

Allergic fungal rhinosinusitis (AFRS) is a severe form of eosinophilic nasal polyposis with critically inadequate treatment options for the 10% of chronic rhinosinusitis participants affected by the disease. Occlusive eosinophilic mucus and severe nasal polyposis presents in early adulthood, with an unrelenting course marked by sinus expansion and pressure-induced dehiscence of the surrounding orbit and skull base. Despite appropriate therapies with oral/topical corticosteroids, saline irrigations and comprehensive sinus surgery, nasal polyps aggressively recur, frequently within months of surgery. Medical options beyond topical and systemic steroids are limited. Neither antifungal nor allergen immunotherapy are beneficial. Due to persistent sinonasal inflammation, patients with AFRS receive an average of three corticosteroid bursts per year and revision sinus surgery every 42 months.

Rationale

In addition to the activation of type 2 inflammatory mediators found in other CRSwNP phenotypes, AFRS is uniquely characterized by an exaggerated activation of the adaptive immune response with serum IgE levels often above 1000 kU/L and defined by an upregulation of fungal specific IgE levels [1]. Marked eosinophilic inflammation is found throughout the upper airway, and the degree of mucosal eosinophil infiltration has been repeatedly reported as a potent predictor of poor surgical outcomes. We therefore hypothesize that dupilumab, a human monoclonal antibody that targets the type-2 inflammatory cascade, is a safe and effective treatment for nasal polyps as add-on therapy following endoscopic sinus surgery.

AFRS represents an extreme form of type 2 inflammation. In a study of immune profiling in 130 participants with different CRS subtypes [2], inflamed sinus mucosa from AFRS participants demonstrated increased local IgE levels when compared to other subtypes, including CRSwNP. While all subtypes demonstrated increased levels of canonical type 2 inflammatory markers, only AFRS demonstrated markedly increased IL-4 levels. Other studies have also reproduced increased mucosal levels of allergen-specific IgE when compared to other CRS subtypes that was not limited to fungal antigens.

The same authors more recently sought to describe the gene expression variations in AFRS that distinguish it from CRSwNP [3]. In a cohort of 86 patients (37 AFRS, 34 CRSwNP, 15 healthy controls), AFRS tissue demonstrated nearly 3,000 unique gene expression variations, while CRSwNP only demonstrated 30. These unique gene expression variations in AFRS were strongly linked with T helper 2 inflammation, co-stimulatory signaling, and T-cell receptor signaling.

Recent Phase III trials with dupilumab have excluded AFRS given the above uniqueness of AFRS from other CRSwNP phenotypes and its regional geographic distribution, despite the exaggerated levels of type-2 inflammatory mediators such as IL-4 and IL-13. In addition, all trials to date have included patients who were at least 6 months removed from a prior sinus surgery. However, the efficacy of the combination of sinus surgery followed by dupilumab has yet to be evaluated in AFRS and exemplifies an attractive treatment regimen for this highly recalcitrant disease.

IMP Mechanism of Action

Dupilumab is a humanized monoclonal antibody that binds to the alpha-subunit of IL4 and IL13 receptors, two key mediators of type-2 inflammation. This represents the first and only dual inhibitor of IL-4 and IL-13. Receptor binding reduces expression of these proinflammatory markers, ultimately leading to decreased total and specific IgE, eosinophil activation, and trafficking.

3. Study Objectives and Endpoints

3.1 Primary Objectives

on initially objectives				
Co-Primary objectives	Endpoint/variable(s)			
	Change from baseline at 52 weeks both within			
	and between treatment and placebo arms			
Determine the efficacy of dupilumab in	Endoscopic modified Lund-Kennedy			
controlling sinonasal inflammation and	(mLK) score			
preventing nasal polyp recurrence after				
complete sinus surgery for AFRS				
 Evaluate the effect of dupilumab on 	• Incidence of oral corticosteroid utilization			
oral corticosteroid utilization following	per participant			
complete sinus surgery for AFRS				

3.2 Secondary Objectives

Secondary objectives	Endpoint/variable(s)	
	Change from baseline at 52 weeks both within	
	and between treatment and placebo arms	
To evaluate the effect of dupilumab on:		
Prevention of revision surgery for AFRS	Prevalence of revision sinus surgery for recurrent nasal polyps, and comparison of survival curves	
Secondary objective measures of sinonasal	• Endoscopic nasal polyp score (NPS)	
inflammation following sinus surgery	CT generated Lund-MacKay score	
• Lower airway dysfunction following sinus surgery in the subgroup of participants with asthma (~25%)	Spirometry	
• Upper and lower airway, disease-specific,	• 22-item sinonasal outcomes test (SNOT-22)	
health-related quality of life	Asthma Control Questionnaire (ACQ)	
Reducing utilization of rescue medications for acute exacerbations of CRS following sinus surgery	 Prevalence of oral / topical corticosteroid utilization per treatment cohort Incidence of oral / topical antibiotic utilization per subject Prevalence of oral / topical antibiotic utilization per treatment cohort 	

Other secondary objectives	Endpoint/variable(s)
	Change from end of treatment (EOT) to end of

	study (EOS)
To evaluate the effect of dupilumab on:	
Objective measures of sinonasal	Endoscopic modified Lund-Kennedy
inflammation following sinus	(mLK) score
surgery	• Endoscopic nasal polyp score (NPS)
• Upper and lower airway, disease-specific,	• 22-item sinonasal outcomes test (SNOT-22)
health-related quality of life	Asthma Control Questionnaire (ACQ)

3.3 Safety Objectives

Safety objective	Endpoint/variable(s)
Assess the safety of dupilumab after sinus	Continual reporting of events of special
surgery	interest (ESIs) and serious adverse events
	(SAEs)
	Physical examination

3.4 Exploratory Objectives

Exploratory objectives	Endpoint/variable(s)
Generation of novel AFRS biobank to support	Exploratory biomarker parameters:
future study of predictive biomarkers	- Serum and plasma
associated with positive clinical outcomes	- Whole blood
following IMP	- Nasal secretions
	- Nasal polyp biopsies

4. Study Intervention/Investigational Agent

4.1 Overall Design

This is a multi-center, randomized, double-blinded, placebo-controlled, parallel group study to evaluate the efficacy of dupilumab 300mg administered subcutaneously (SC) every 2 weeks versus placebo in participants with AFRS following planned sinus surgery.

132 participants will be randomized to receive dupilumab 300mg SC or matching placebo while on a background of intranasal corticosteroid sprays twice daily. Patients will be stratified by study site and by baseline comorbid asthma status (yes vs no). ~25% of the randomized participants will have comorbid asthma.

Eligible participants will enter a screening/run-in period on twice daily nasal saline irrigations followed by INCS spray for 2-6 weeks prior to planned sinus surgery. Participants may be consented and enrolled at any time during this 2-6 week run-in period, provided the failure of appropriate medical therapy has been documented as outlined in the inclusion criteria. Eligible participants already on study background therapy for at least two weeks may be consented and enrolled during the pre-surgery period.

Both saline irrigations/INCS and sinus surgery will be completed per standard of care (SoC) and not according to the study protocol. Patients who continue to meet eligibility criteria following surgery will be randomized 1:1 before Visit 3 (Day 0) when they receive placebo or dupilumab 300mg SC every 2 weeks. Patients will receive a total of 26 doses of IMP, via either study

personnel (Visit 3-6 at W0, 12, 24 and 36) or home-administration (W2, 4, 6, 8, 10, 14, 16, 18, 20, 22, 26, 28, 30, 32, 34, 38, 40, 42, 44, 46, 48, 50) to maintain a 2-week treatment schedule. Patient compliance will be recorded via text messages the day of scheduled home administration, as well as monthly phone calls and collection of used syringes during scheduled study visits (Visit 4-7 at W12, 24, 36 and 52). An EOT visit will be conducted at Week 52 (Visit 7). Patients will then be monitored on daily saline irrigation and INCS spray for 12-weeks to evaluate potential disease recurrence after discontinuation of IMP. An EOS visit will be conducted at Week 64 (Visit 8).

Participants will return to their respective study site for dosing visits (Visit 3-6), EOT and EOS for evaluation of efficacy and safety. Collection of optional blood and nasal secretions for exploratory biomarker analysis will be completed at study visits 1, 3, 4, 5, 7 and 8. Nasal polyp tissues will be collected at time of surgery (Visit 2).

Sinus surgery will be completed per SoC. Study protocol will determine cohort assignment (use of IMP versus placebo) with all other SoC interventions allowed throughout the entire study. Physician prescribed SoC medications for the treatment of nasal polyps include INCS sprays and nasal saline irrigations. Rescue medications are allowed per the treating physician's discretion.

Rescue medications (topical/oral corticosteroids, topical/oral antibiotics, or revision sinus surgery) will be allowed as deemed clinically necessary for the treatment of an acute exacerbation of CRS (AECRS) by the treating physician. See Table 3 for standardized criteria to diagnose AECRS [1]. If at any point a subject meets discontinuation criteria, an early discontinuation visit will be performed (see Section 8.1- Discontinuation of study treatment).

Table 3: Diagnostic Criteria for AECRS

- Duration of symptoms ≥7 days
- Total SNOT-22 score increased >9 from baseline
- Objective evidence of sinonasal inflammation by nasal endoscopy or CT scan

AECRS; Acute exacerbation of chronic rhinosinusitis

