4.7 Randomization and blinding

Randomized participants will be stratified by enrollment site. Randomization will be assigned on a 1:1 basis to treatment group (dupilumab 300 mg every 2 weeks) or placebo. The study data team will prepare a randomization list based on computer-generated random numbers retrieved using a randomization procedure available in statistical packages such as SAS. Block randomization with varying block sizes will be employed to ensure that equal numbers of treatment and placebo participants occur within strata (site) and are balanced with respect to observed and unmeasured baseline factors.

This is a double-blind investigation. Patients, treating physicians and local study personnel will not be aware of cohort allocation.

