14.4 Randomization

After eligibility is established and consent is obtained, the participants will be randomized on a 1:1 basis to treatment (dupilumab 300 mg every 2 weeks) or placebo. The study biostatistician will prepare a randomization list based on computer-generated random numbers retrieved using a randomization procedure available in statistical packages such as SAS. Block randomization with varying block sizes will be employed to ensure that equal numbers of treatment and placebo participants occur within strata (site) and are balanced with respect to observed and unmeasured baseline factors.

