14.6 Primary Analysis

To examine changes in the co-primary outcomes, the modified Lund-Kennedy score and the incidence of oral corticosteroid utilization per participant, a mixed effects longitudinal model will be fit that includes group (dupilumab, placebo) as a between participants factor and time (randomization through post-treatment period) as a categorical within participants factor plus their interaction term. Time is treated as categorical so that we can use the group-time interactions with the time main effect to estimate and test intent-to-treat (ITT) group differences at each time point, with 52 weeks as our primary ITT test. As randomization is stratified by site, site will also be included in the model. This mixed effects model allows incorporation of a random intercept term for each subject, different numbers of measurements (in case a visit is skipped), and the choice of appropriate variance-covariance structure. The mixed model will also permit identification of any significant changes in the post-treatment period from 52 to 64 weeks. This primary mixed model will incorporate all subject's randomized.

The primary objective will be assessed by testing this null hypothesis: treatment with Dupilumab post-surgery is equivalent to treatment with placebo post-surgery at 52-week end of treatment. The additional time point at 64 weeks is included in the model to ensure efficient evaluation of both co-primary outcomes at the EOT and 12 weeks after EOT. Significant changes between weeks 52 and 64 will be examined by linear contrast. We will test the following null hypotheses against two-sided alternatives:

- H₀₁: there is a lack of difference between the changes in mLK from baseline to 52 weeks and from baseline to 64 weeks for the untreated.
- H_{02} : there is a lack of difference between the changes in mLK from baseline to 52 weeks and from baseline to 64 weeks for the treated.
- H_{03} : the treatment effect dissipates between 52 and 64 weeks.

The primary estimand for the primary endpoint is the composite/treatment policy strategy. The intercurrent events will be handled as follows:

- Undergoing sinus surgery for AFRS: data after surgery will be assigned the worst possible score (composite strategy)
- Taking SCS or other rescue medications: data collected after use will be used in the analysis (treatment policy strategy)

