14.7 Secondary and Exploratory analyses

In a secondary analysis, a similar mixed model as described above will be fit that includes the subset of participants who are receiving treatment (dupilumab or placebo) for both nostrils. This model will incorporate nesting factors to identify repeated measures by subject and by nostril.

In an exploratory analysis, we will also compare the proportion of participants whose modified Lund- Kennedy score improved by greater than or equal to 2 units. For participants who undergo sinus surgery for AFRS prior to Week 52, non-responder imputation will be used. We will utilize a Chi-square or Fisher's exact test to examine if this proportion is significantly different by treatment group (dupilumab or placebo) at 52 weeks.

For the continuous secondary outcomes (e.g. SNOT-22 score, NPS, FEV1), a mixed effects longitudinal model will be fit that includes group (dupilumab, placebo), time (randomization through post-treatment period), and their interaction term in a similar fashioned as described for the primary outcome modified Lund-Kennedy score. For the secondary outcomes that compare the number of participants requiring rescue treatment and the number of adverse events (safety) over 52 weeks, similar mixed effects models will be fit but with consideration of a Poisson distribution (as opposed to normal distribution). The mixed effects models for both primary and secondary outcomes will permit the inclusion of any significant potential confounders.

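### Section 4.1 stratifies randomisation by site and asthma, while Sections 4.7, 14.4 and 14.6 use site only: either the primary model omits a stratum, or the asthma balance stated in 4.1 is not delivered

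*Combined protocol and SAP*

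**What the plan says.** - Section 4.1 (Overall Design) names two factors: "Patients will be stratified by study site and by baseline comorbid asthma status (yes vs no". It adds an expected share of about "25% of the randomized participants will have comorbid asthma".
- Section 4.7 (Randomization and blinding) names one: "Randomized participants will be stratified by enrollment site". It then describes permuted blocks of varying size within that single stratum.
- Section 14.4 (Randomization) repeats the site-only scheme; its blocks are meant to ensure that equal numbers of "treatment and placebo participants occur within strata (site) and are balanced with respect to observed and unmeasured baseline factors".
- Section 14.6 (Primary Analysis) takes its covariate from the same premise: "As randomization is stratified by site, site will also be included in the model". The other terms are group, time and their interaction, with a random intercept per participant.
- Section 14.7 leaves a general opening: "The mixed effects models for both primary and secondary outcomes will permit the inclusion of any significant potential confounders". No model in 14.6 or 14.7 names asthma.

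Asthma status also defines an analysis population. Section 3.2 sets a lower-airway objective, measured by spirometry, in the asthma subgroup. Section 5.3 restricts the ACQ to participants with asthma.

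**The concern.** These are all current sections, so the mismatch is not a leftover from the amendment log. A reader cannot tell from the document how participants are allocated, and the covariates of the primary model depend on the answer.

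The two possible consequences are alternatives.

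- **(a) The list follows 4.1.** Balance on asthma is protected, but the 14.6 model leaves out a factor used in the allocation. That breaks the section's own rule that a stratum belongs in the model. The standard errors are then too wide to the extent that asthma predicts the outcome.
- **(b) The list follows 4.7 and 14.4.** The model matches the list, but 4.1 claims a design property that the trial lacks. The arm split among participants with asthma is left to chance, and no whole-cohort model is committed to adjusting for it.

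**Working it through.** **Inputs from the document.** 132 randomised 1:1, so 66 per arm; 3 sites with 44 intended at each (Section 8); about 25% with asthma (Section 4.1), so 0.25 × 132 = 33; difference 2 and SD 3.5 on mLK, two-sided 0.05, 90% power (Section 14.1).

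**Assumptions not in the document.** Block sizes of 2/4/6 or 4/6/8; exactly 11 participants with asthma per site; share of mLK variance explained by asthma (R²) between 0 and 0.20.

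**1. The plan's own figure.** n per arm = 2(1.96 + 1.2816)² × 3.5² / 2² = 64.4, so 65 by the normal formula; the noncentral t gives 66. Power at 66 per arm is 90.7% (normal) or 90.3% (t). The stated 66 per group reproduces, and nothing below changes it.

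**2. Reading (a): site by asthma list, asthma not in the model.** With asthma balanced by design, the true standard error is √(1 − R²) times the one that the model reports. This is a normal approximation for the week-52 mLK comparison, with the planning SD of 3.5 taken as the total SD.

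- Reported SE = 3.5 × √(2/66) = 0.609.
- Actual alpha = 2[1 − Φ(1.96/√(1 − R²))].
- Power with asthma omitted = Φ((2 − 1.96 × 0.609)/(0.609√(1 − R²))).
- Power with asthma included = Φ(2/(0.609√(1 − R²)) − 1.96).

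| Assumed R² | Actual alpha, asthma omitted | Power, omitted | Power, included |
|---|---|---|---|
| 0 | 0.050 | 90.7% | 90.7% |
| 0.05 | 0.044 | 91.3% | 92.0% |
| 0.10 | 0.039 | 91.8% | 93.3% |
| 0.20 | 0.028 | 93.0% | 95.6% |

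Omission costs 0.7 to 2.6 percentage points of power over R² of 0.05 to 0.20. Power stays above the planned 90% throughout.

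**3. Reading (b): site-only list.** The number with asthma on dupilumab is approximately hypergeometric (132 participants, 33 with asthma, 66 on dupilumab).

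- Mean 16.5; SD = √(66 × 0.25 × 0.75 × 66/131) = 2.50.
- Two-sided chance of 20:13 or worse: 0.228. Of 21:12 or worse: 0.107. Of 22:11 or worse: 0.043.

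A simulation of 10,000 trials per scheme agrees. Site-only blocks give a 95% range of 12 to 21 on dupilumab (SD 2.5), with 20:13 or worse in about 23% of trials. Site by asthma strata give 15 to 18 (SD 0.9 to 1.0), with 20:13 or worse in less than 0.1%.

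**4. Cost of an uneven split in the asthma-only analyses.** Variance relative to an even split is (1/a + 1/b)/(2/16.5).

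- 20:13: (0.0500 + 0.0769)/0.1212 = 1.047, about 5% more variance.
- 21:12: (0.0476 + 0.0833)/0.1212 = 1.080, about 8% more variance.

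**5. Imbalance in the whole cohort.** At 20:13, the asthma share is 20/66 = 30.3% in one arm and 13/66 = 19.7% in the other, a gap of 7/66 = 10.6 percentage points. No model in 14.6 or 14.7 is committed to adjusting for it.

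**The case against.** The strongest reply is that little is at stake. Reading (a) errs on the safe side. Under reading (b), randomisation keeps every comparison unbiased on average, and chance imbalance is already covered by the test's type I error. Section 14.10 says that the study is not designed to show significant differences in secondary outcomes, which lowers the weight of the asthma subgroup. Section 14.7 allows confounders to be added. If the list is site-only, an asthma covariate is a sensible preference and not the correction of an error.

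Most of this stands, and it limits the size of the point. It does not remove the contradiction. The permission in 14.7 does not cure it either: it names no variable and makes entry depend on significance, which is not pre-specification.

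A reader might also infer more than the document supports:

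- **That chance asthma imbalance confounds the lower-airway results.** Spirometry and ACQ are assessed only in participants with asthma, so asthma status is constant there. An uneven split costs precision only.
- **That Section 7.3 shows asthma driving the oral corticosteroid co-primary.** That text concerns exacerbations in the run-in before surgery, while the co-primary counts use after surgery. A later effect of asthma is plausible, but the document gives no figure for it.
- **That an asthma covariate repairs everything.** In an asthma-only analysis it is a constant and does nothing. It cannot alter a subgroup split that has already occurred.

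**Conclusion.** The inconsistency is real: Section 4.1 gives two strata, and Sections 4.7, 14.4 and 14.6 give one. Exactly one of the two consequences applies, and the document does not show which. It would be wrong to read them as joint harms.

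Under (a), the primary mLK test is mildly conservative, with alpha about 0.044 to 0.028 over an assumed R² of 0.05 to 0.20. Type I error is not inflated. Under (b), a split of 20:13 or worse among about 33 participants with asthma has about a 23% chance, at a cost of about 5% in subgroup variance (8% at 21:12) and no bias. Asthma imbalance then goes unadjusted in the whole-cohort outcomes.

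The sample size is unaffected either way. The figures rest on the 25% asthma share being met and, for (a), on an R² that the document does not give; the simulated ranges also rest on assumed block sizes and an even spread of asthma across sites. This should be corrected because it is cheap and fixes the primary model's covariates in advance, not because it threatens the main conclusion.

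**What to change.** 1. Establish which list is in use and state that one set of strata in Sections 4.1, 4.7, 14.4 and 14.6. If the list is site-only, correct 4.1 and leave the ongoing allocation as it is.
2. In either case, pre-specify baseline asthma (yes/no) and site as fixed effects in the 14.6 models for both co-primary outcomes and in the 14.7 models for the whole-cohort secondary outcomes. Do this before unblinding, so that the choice cannot appear to depend on results.
3. State that the asthma term does not apply to the asthma-only spirometry and ACQ analyses.

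The cost is an amendment to the wording and one covariate, which should be available from the medical history taken at Visit 1 (Table 1). No patients, visits or procedures are added. If the list is site by asthma, 3 sites × 2 levels gives 6 strata, which is workable for blocked randomisation with 132 participants.
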